6.3.4 Rationale for Endpoints

The endpoints were chosen as applicable measures of device safety and effectiveness because of their similarity to those of interest in the literature and to those of interest to FDA⁴ and several physician society groups.⁴⁹

6.4 Variables to be Measured to Demonstrate Achievement of Endpoints

Independent core laboratories (to be designated) will be used to provide detailed analysis of imaging data collected.

The clinical data and imaging measurements will be collected on standardized case report forms (CRFs), which may serve as source documents. The schedule for assessments is summarized in Table 6.1.

Table 6.1. Data collection schedule

	Pre-procedure ^a	Placement	Post-procedure ^b	3 months post-placement	6 months post-placement	12 months post-placement	18 months post-placement	2 years post-placement	Pre-retrieval ^c	Retrieval	1 month post-retrieval
Chest CT or other imaging to document pre-procedure PE in patients with clinical indications	X ^a										
Medical history	X ^d										
Clinical assessment	X ^d		X	X		X		X			X
Duplex ultrasound	X ^e					X					
Diagnostic imaging		X ^f									
Venacavagram										X ^g	
Abdominal CT with contrast						X		X			
X-ray (2-view device)			X ^{h,i}			X ⁱ			X ⁱ		
Telephone contact					X		X				

^aImaging to document PE (i.e., pulmonary arteriography, cross-sectional imaging, or ventilation/perfusion lung scan) in accordance with the institution's standard of care; the imaging will be collected

^bPotential adverse events following filter placement must be documented by an appropriate imaging modality (e.g., suspected DVT should be assessed by bilateral lower extremity ultrasound and/or CT venography, suspected PE should be assessed by pulmonary arteriography, cross-sectional imaging, or ventilation/perfusion lung scan, and suspected perforation should be assessed by CT)

^cIf a 2-view device X-ray was collected within 30 days prior to retrieval, an additional X-ray would not be required pre-retrieval

^dCan be collected up to 6 weeks prior to the index procedure

^eDuplex ultrasound of the IVC, bilateral pelvic veins, and bilateral lower extremity veins. For patients in whom a CT with contrast was performed as part of routine care within 2 weeks of the filter placement procedure, the CT may be used to assess for thrombus in vein segments visualized on CT. For cases in which a physician feels it is in the best interest of the patient to forego the ultrasound exam so the filter may be placed immediately and/or in which a duplex ultrasound may not be physically possible prior to filter placement (e.g., patients with trauma to the pelvis), the venogram may be used to assess for thrombus in vein segments visualized on the venogram. If segment(s) of vein are not assessed before the filter is placed, assessments are to be completed within one day after the placement procedure. Assessments of all vein segments of interest are to be completed, unless a patient's injuries prevent examination of one or more vein segment(s)

^fImaging performed pre-placement to verify anatomical study criteria and post-placement to verify the position of the filter

^gVenacavagram performed pre- and post-retrieval

^hPatients undergoing bedside filter placement in whom a 2-view device X-ray could not be obtained prior to discharge must have a 2-view device X-ray within 45 days post-placement

ⁱ2-view device X-ray may be substituted with high quality still shot from venacavagram (2-view) to assess device integrity

6.5 Measures to be Taken to Avoid or Minimize Bias

This study is designed as a prospective clinical trial to minimize bias in analyzing the results. Specifically, the study will utilize event adjudication by an independent clinical events committee and imaging analysis by a centralized core laboratory to minimize bias in analyzing the results. Patients requiring temporary or permanent IVC filter placement to prevent PE will be screened consecutively to mitigate selection bias. Investigational sites will maintain a screening log of patients; for patients who are excluded from the study, the log will indicate the primary inclusion/exclusion criterion that is violated. A single institution may enroll up to 20% of the patients in each stratum to minimize bias that may be introduced if the majority of patients are enrolled from one or two large clinical sites. Finally, filter choice will be left to the discretion of the physician.

7.0 Methods

7.1 Patient Consent

Patients who meet the inclusion criterion and none of the exclusion criteria will be invited to participate in this study. All patients eligible for entry into the study will have the study explained to them, as well as potential risks and benefits of their participation in the study. Each patient (or legally authorized representative) who agrees to participate will be required to sign an informed consent document prior to undergoing study-specific testing or the filter placement procedure. If new information is obtained after a patient receives treatment with the device, patients who have not exited the study will be informed about the new information, and will be reconsented at the discretion of the investigators and/or the sites' IRBs/ECs/REBs.

7.2 Point of Enrollment

Patients will be considered enrolled in the study once the filter introducer sheath is inserted below the skin.

7.3 Medications

Patients should receive medication(s) according to the institution's standard of care and/or at the physician's discretion, based on each patient's individual medical condition. The use of antiplatelet and anticoagulation medications should be recorded on appropriate CRFs.

7.4 Pre-procedure

A pre-procedure clinical assessment will be completed (up to 6 weeks prior to the index procedure) including documentation of medical comorbidities and assessment of medications. Duplex ultrasound of the IVC, bilateral iliac veins, and bilateral lower extremity veins will be performed; presence of DVT will be documented on the appropriate CRF. For patients in whom a CT with contrast was performed as part of routine care within 2 weeks of the filter placement procedure, the CT may be used to assess for thrombus in vein segments visualized on CT. For cases in which a physician feels it is in the best interest of the patient to forego the ultrasound exam so the filter may be placed immediately and/or in which a duplex ultrasound may not be physically possible prior to filter placement (e.g., patients with trauma to the pelvis), the venogram may be used to assess for thrombus. If segment(s) of vein are not assessed before the filter is placed, assessments are to be completed within one day after the placement procedure. Assessments of all vein segments of interest are to be completed, unless a patient's injuries prevent examination of one or more vein segment(s).

Patients with suspected PE should undergo appropriate assessment for the presence of PE, including appropriate imaging (i.e., pulmonary arteriography, cross-sectional imaging, or ventilation/perfusion lung scan), according to the institution's standard of care. This imaging will be collected and results of these assessments will be documented on the appropriate CRF.

7.5 Filter Placement Procedure

- Diagnostic imaging will be performed prior to study enrollment to verify anatomical study criteria.
- Only one Cook IVC filter should be placed in each patient. The Cook IVC filter should be implanted in accordance with the respective IFU (i.e., caudal to the renal veins).
- Completion imaging will be performed to assess filter position (including tilt) and to assess the vena cava for evidence of injury.

7.6 Post-Filter Placement/Pre-Discharge

Post-placement care includes observation and discharge according to institutional standard of care and completion of clinical and medication assessments. In addition, a 2-

view device X-ray will be performed prior to hospital discharge; the X-ray should be performed in AP and LAT views. Patients undergoing bedside filter placement in whom a 2-view device X-ray could not be obtained prior to discharge must have a 2-view device X-ray within 45 days post-placement.

7.7 Post-Placement Follow-up

Follow-up windows are intended as guidelines only. They are not absolute and are not intended to limit data collection due to scheduling conflicts.

- *3 Months Post-Placement (90 ± 15 days):* Office visit including an assessment of the need for continued filtration, and an assessment of medications, hospitalizations, and medical conditions.
- *6 Months Post-Placement (180 ± 30 days):* Telephone contact by the clinical site to assess hospitalizations and medical conditions. Up to three attempts should be made to contact the patient.
- *12 Months Post-Placement (365 ± 30 days):* Office visit including an assessment of the need for continued filtration, and an assessment of medications, hospitalizations, and medical conditions. An abdominal CT with contrast to assess filter leg interaction with the IVC, a 2-view device X-ray to assess device integrity (the X-ray should be performed in AP and LAT views), and duplex ultrasound (IVC, bilateral pelvic veins, and bilateral lower extremity veins) to assess thrombus/DVT will be performed.
- *18 Months Post-Placement (540 ± 60 days):* Telephone contact by the clinical site to assess hospitalizations and medical conditions. Up to three attempts should be made to contact the patient.
- *2 Years Post-Placement (730 ± 60 days):* Office visit including an assessment of the need for continued filtration, and an assessment of medications, hospitalizations, and medical conditions. An abdominal CT with contrast to assess filter leg interaction with the IVC will be performed.

The need for continued filtration will be assessed based on each patient's overall medical condition. The decision to proceed to a retrieval attempt should also be based on factors such as the patient's ability and willingness to undergo the retrieval procedure and the physician's assessment of the risk/benefit ratio associated with the retrieval procedure.

If at any time during follow-up a patient presents with adverse clinical symptoms potentially related to his/her indwelling filter or the development of DVT/PE, appropriate assessments and treatment should be conducted according to the institution's standard of care. Clinical and imaging findings will be documented on the appropriate CRFs. For example:

- If the physician suspects a vena cava perforation, an abdominal CT with contrast will be performed to assess filter leg interaction with the IVC.
- If the physician suspects DVT, the DVT will be documented by duplex ultrasound, contrast venography, CT, or MR venography.
- If the physician suspects PE, the PE will be documented by pulmonary arteriography, cross-sectional imaging (e.g., CT, MRI), or ventilation/perfusion lung scan.

7.8 Filter Retrieval Procedure

The Cook IVC filters may be retrieved if clinically indicated.

Before retrieval, the following will be performed:

- Two-view device X-ray to assess device integrity; X-ray should be performed in AP and LAT views; and
- Venacavagram to assess filter position, presence and extent of thrombus in the filter, and IVC wall morphology.

If a 2-view device X-ray was collected within 30 days prior to retrieval, an additional pre-retrieval X-ray would not be required. The venacavagram will be collected procedurally, just prior to filter retrieval.

Filter retrieval should not be attempted in the instance that significant trapped thrombus (i.e., > 25% of the cone volume) is observed in the filter. Filter retrieval should be performed using the Günther Tulip[®] Retrieval Set and in accordance with the IFU. Following retrieval, the IVC will be assessed by venacavagram.

If the filter retrieval attempt is unsuccessful, the patient will continue his/her post-placement follow-up schedule, indexed to the filter placement procedure. Another filter retrieval attempt can be made at a later date, depending on the patient's medical condition.

7.9 Post-Retrieval Follow-up

If the filter retrieval attempt is successful, the patient will assume the post-retrieval follow-up schedule. Follow-up windows are intended as guidelines only. They are not absolute and are not intended to limit data collection due to scheduling conflicts.

- *1 Month Post-Retrieval (30 ± 15 days)*: Office visit including an assessment of medications, hospitalizations, and medical conditions.

Suspected PE post-retrieval must be objectively confirmed by imaging (i.e. pulmonary arteriography, cross-sectional imaging, or ventilation/perfusion lung scan) or at autopsy and will not count against the primary endpoint.

7.10 Duration of Study and Patient Participation

Patients will be followed until 1 months after successful filter retrieval or until study completion 2 years after filter placement. Total study duration (from study initiation through patient enrollment and follow-up) is expected to be less than 5 years.

7.11 Imaging

An imaging manual will be provided by the sponsor. The imaging criteria specified in the manual should be followed for all imaging required per this CIP. Any imaging performed at pre-procedure, filter placement, filter retrieval, or at any time during follow-up to evaluate potential adverse events will be recorded on the appropriate CRF and submitted to the data coordinating center.

7.12 Criteria and Procedures for Withdrawal

A patient may decide to withdraw from the study at any time without prejudice or loss of care. The patient should notify the investigator of his/her desire to withdraw. The investigator will notify the sponsor. The investigator may also decide to withdraw a

patient from the study at any time based on medical judgment. In all instances of withdrawal, data collected up to the time of patient withdrawal, including the study exit form, should be submitted to the data coordinating center, and should include the reason why the patient has been withdrawn from the study. Patients withdrawn from the study should be followed according to institutional standard of care.

In the event a patient cannot be contacted for post-treatment assessments, at least three attempts should be made to contact the patient, and these efforts should be documented on the appropriate CRF. If a patient misses post-treatment assessments and cannot be located, a lost to follow-up entry should be submitted.

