7.13 Participation Endpoints of the Study

A patient's participation in the study will end after any of the following:

- Completion of all scheduled clinical and imaging evaluations to 1 month post-retrieval or 2 years post-placement;
- Device not implanted;
- Patient withdrawal or lost to follow-up;
- Closure of the study; or
- Patient death.

Any data collected on the patient up to a participation endpoint (or until all queries involving the patient are resolved) may be used in the study.

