8.3 Sample Size

The study is designed to enroll 320 patients in the Celect[®] filter stratum (to evaluate the safety and effectiveness hypotheses) and up to 150 patients in the Günther Tulip[®] filter stratum at up to 40 sites globally. At least half of the study patients in the Celect[®] filter stratum will be enrolled at US sites.

For the primary effectiveness endpoint, based on what are considered clinically acceptable rates for technical placement success and new symptomatic PE in the overall

population, a performance goal of the rate of technical placement success and 12-month freedom from new symptomatic PE while a filter is indwelling was established to be 90%.⁴⁸ Additionally, based on the data from previous Cook sponsored studies (as summarized in Section 4.0), the rate of technical placement success and 12-month freedom from new symptomatic PE while a filter was indwelling was estimated to be 98.4% for the Celect[®] filter stratum. A sample size of 70 patients will be required to assess the primary effectiveness hypothesis for the Celect[®] filter stratum, with a one-sided exact binomial test, at a type I error rate of 0.025, and a power of 0.9. The calculation was performed with the SAS UnifyPow macro.

For the primary safety endpoint, based on what are considered clinically acceptable rates for each complication in the overall population, a performance goal of the rate of 12-month freedom from major adverse events was established to be 80%.⁴⁸ Based on the data from previous Cook-sponsored studies (as summarized in Section 4.0), the rate of 12-month freedom from major adverse events was estimated to be 92.2% for the Celect[®] filter stratum. A sample size of 88 patients will be required to assess the primary safety hypothesis for the Celect[®] filter stratum, with a one-sided exact binomial test, at a type I error rate of 0.025, and a power of 0.9. The calculation was performed with the SAS UnifyPow macro.

Based on sample size calculations, a minimum of 88 patients in the Celect[®] filter stratum will be required to evaluate the safety and effectiveness endpoints. Cook intends to enroll 320 patients in the Celect[®] filter stratum; this sample size allows for an attrition rate of 72% (i.e., 60% of filters to be retrieved prior to 12 months and an additional 12% of patients who may die, withdraw, or become lost to follow-up). The study may also enroll up to 150 patients in the Günther Tulip[®] filter stratum.

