8.4 Missing Data

If the amount of missing data does not result in a reduction of analyzable patients to a number that is below that which is required for sufficient statistical power of the primary endpoints, case deletion will be the primary method to handle missing data.

However, if missing data results in a reduction of analyzable patients to a number that is lower than what is required for sufficient statistical power of the primary measures, then missing data will be addressed using multiple imputation with best available data, if

appropriate. This method will be used to predict missing endpoint and imaging data. Previous clinical trial experience suggests that some portion of the imaging data may not meet the criteria for accurate review by the core laboratory; however, it is recognized that the investigator uses this information to provide the best possible care for the patient. Therefore, it is reasonable to substitute any missing core laboratory measurements with the corresponding measurements made by the investigator or institutional staff.

Statistical imputation strategies originating from Schafer may also be used, supplemented with notes provided by Shafer.^{51,52} All missing endpoint and covariate data will be imputed with the values simulated from their respective empirical distributions. The computations (with no covariates) will be performed using five imputed datasets and PROC MI and PROC MIANALYZE in SAS version 9.3, or WinBUGS 1.4 or later. Unless evidence suggests otherwise, missing at random data will be assumed.

Additional analyses may also be performed to address missing data, including tipping point analysis.

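### Outcome collection is not provided for after any withdrawal, including withdrawal by the investigator, although a patient withdrawn before retrieval still carries the filter; if withdrawal is related to worse outcome, the 12-month rates are too favourable

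*Combined protocol and SAP*

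**What the plan says.** Section 7.12 lets patients withdraw themselves and lets the investigator withdraw a "patient from the study at any time based on medical judgment". No criteria are listed. The data rule is the same for both: "In all instances of withdrawal, data collected up to the time of patient withdrawal, including the study exit form, should be submitted", together with the reason. After that, "Patients withdrawn from the study should be followed according to institutional standard of care".

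Section 7.13 lists "Patient withdrawal or lost to follow-up" among the events that end participation, and adds: "Any data collected on the patient up to a participation endpoint (or until all queries involving the patient are resolved) may be used".

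For the analysis, Section 8.1.2 tests safety with a Kaplan-Meier estimate at 12 months against 80%. Section 8.1.1 tests effectiveness with an exact binomial test against 90%. Under Section 8.4, while enough patients remain analysable for power, "case deletion will be the primary method to handle missing data"; below that number, multiple imputation is used. "Unless evidence suggests otherwise, missing at random data will be assumed". A tipping-point analysis is named there only as something that may be done.

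Section 8.3 allows for "60% of filters to be retrieved prior to 12 months and an additional 12% of patients who may die, withdraw, or become lost to follow-up".

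**The concern.** Leaving the study does not end exposure. Retrieval depends on clinical indication (Section 7.8) and is not tied to withdrawal, so a patient withdrawn before retrieval can still have a PE or a major adverse event with the filter in place. These are the events that the two primary endpoints count (Sections 6.3.1 and 6.3.2).

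Censoring, case deletion and imputation under missing at random all assume that the patients who leave would have fared like comparable patients who stay. Withdrawal on medical judgment is the case where that assumption is least secure, because the reason may be the patient's condition. If those patients do worse, 12-month freedom from major adverse events and from symptomatic PE is overstated. Both endpoints are compared with fixed goals, so no second arm carries the same bias. The plan also draws no line between stopping study visits and withdrawing consent for data use, so events that could be learned from a telephone call or a hospital record are given up.

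**Working it through.** **1. The plan's own figures.** With a one-sided exact binomial test at 0.025:
- Safety (80% against 92.2%), n = 88: at least 78 successes needed, actual alpha 0.0238, power 0.919.
- Effectiveness (90% against 98.4%), n = 70: at least 68 successes needed, alpha 0.0242, power 0.898, close to the stated 0.9.
- Attrition: 320 × (1 − 0.72) = 89.6, which covers 88.

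**2. How many patients could be affected.** 0.12 × 320 = 38.4, about 38. This covers deaths, withdrawals and losses together, so withdrawals are fewer. No split is given.

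**3. Illustration at the edge of the safety goal.** Assumptions, none from the documents unless stated:
- n = 320 and 60% retrieved by 12 months (both Section 8.3), with exponential retrieval times and censoring at retrieval.
- A share w withdrawn, at times uniform over 12 months, with 12-month risk RR times that of the others.
- True overall freedom of exactly 80%, so the risk in the others is 0.20 / (1 − w + w × RR). At RR = 2 this is 0.20/1.04 = 19.2%, 0.20/1.08 = 18.5% and 0.20/1.12 = 17.9% for w = 4%, 8% and 12%.
- A pass if S − 0.8 > 1.96 × SE, with SE taken as S × √((1 − S)/number at risk). The plan names the Peto variance but prints no formula.

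Results at RR = 2 (ranges are the spread over repeated runs):

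| Withdrawn | Timing unrelated: mean KM | False pass | All events after withdrawal: mean KM | False pass |
|---|---|---|---|---|
| 4% | 80.4% | 2.1–2.3% | 81.2% | about 4% |
| 8% | 80.8% | 2.7–2.8% | 82.2% | about 7–8% |
| 12% | 81.1% | 3.1–4.0% | 83.2–83.3% | about 13–14% |

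Non-informative loss gives about 1–2%, below the nominal 2.5%, because this standard error is conservative. At RR = 3 the false-pass rates are 2.9%, 4.4% and 6.0% with unrelated timing. They are about 6%, 16% and 30% if every event follows withdrawal.

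**4. How many unseen failures would reverse a pass.** Exact binomial limits, with expected failures at the planned rates:

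| Patients counted | Endpoint | Failures allowed | Expected among observed | Unseen failures needed among 38 |
|---|---|---|---|---|
| 90 + 38 = 128 | Effectiveness | 6 | 90 × 0.016 = 1.4 | 7 − 1.4 = 5.6 |
| 128 | Safety | 16 | 90 × 0.078 = 7.0 | 17 − 7.0 = 10 |
| 282 + 38 = 320 | Effectiveness | 21 | 282 × 0.016 = 4.5 | 22 − 4.5 = 17.5 |
| 320 | Safety | 49 | 282 × 0.078 = 22 | 50 − 22 = 28 |

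The first two rows count only patients with full 12-month data. The last two also count retrieved patients as observed. At twice the planned risk, the 38 would have 38 × 0.032 = 1.2 effectiveness failures and 38 × 0.156 = 5.9 safety failures. At three times, they would have 1.8 and 8.9. None of these reaches the number needed. The safety rows use the binomial test of Section 8.3 as a stand-in for the Kaplan-Meier test.

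**5. Effect on the reported rates at the planned values.** Suppose all 38 carry twice the risk and go unseen.
- Safety: the true rate is (282 × 0.922 + 38 × 0.844)/320 = 91.3% on all 320, or (90 × 0.922 + 38 × 0.844)/128 = 89.9% on 128, against 92.2% reported.
- Effectiveness: (282 × 0.984 + 38 × 0.968)/320 = 98.2%, or (90 × 0.984 + 38 × 0.968)/128 = 97.9%, against 98.4% reported.

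**The case against.** The other side has several good arguments.

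- **Timing drives the large figures.** The 13–14% and 30% false-pass rates need every event of a withdrawn patient to fall after withdrawal. Events before withdrawal are kept, and some major adverse events, such as access site complications and procedure-related death, can occur early. With unrelated timing and doubled risk the test stays close to its nominal 2.5%. This stands, so both ends of the range are shown.
- **The 12% is not a withdrawal rate.** It includes deaths and losses, which a change to the withdrawal rule would not recover. This stands.
- **Nothing says that problem patients are withdrawn.** A reader might infer that investigators would remove patients whose filter looks troublesome. The documents do not support that: Section 7.7 has filter-related symptoms assessed and recorded, and Section 7.8 keeps a patient on schedule after a failed retrieval. The concern is only that withdrawal may be related to outcome and that the plan could not see it.
- **No sentence says that all collection stops.** That is the combined effect of 7.12 and 7.13, which also allow data to be used until queries are resolved. Nor does every withdrawn patient still have a filter; some may withdraw after retrieval.
- **The plan has partial safeguards.** The reason for withdrawal must be recorded, missing at random is a default that evidence can displace, and a tipping-point analysis is available. But the analysis is optional, and none of these supplies the missing outcomes.
- **A patient's own withdrawal of consent properly ends collection.** This stands, and the fix respects it. The gap is clearest for withdrawal by the investigator.

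**Conclusion.** The point holds as a conditional one. The plan asks for no outcome data after any withdrawal, and its analysis then treats the patient as uninformative. If withdrawal is related to worse outcome, the 12-month freedom rates are biased upward with nothing to offset it.

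The size cannot be fixed from the documents. At a true safety rate of 80% and doubled risk, the mean estimate lies about 0.4 to 1.1 points too high if event timing is unrelated to withdrawal. It lies about 1.2 to 3.3 points too high if all events follow it. The false-pass rate is about 2–4% and about 4–14% respectively. Withdrawal share, risk ratio and timing are all assumptions, and the 12% row is an upper bound.

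A reader might infer that the study is likely to pass wrongly. The documents do not support that. If the planned 92.2% and 98.4% are true, even tripled risk in all 38 patients would not be expected to reverse either result. What remains is a possible overstatement of the reported rates: about 0.9 to 2.3 points for safety and 0.2 to 0.5 for effectiveness under the doubled-risk assumption. That matters for a study meant to answer FDA's safety concerns. The change is worth making because it is cheap and because the data may not be recoverable later.

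**What to change.** In Sections 7.12 and 7.13, separate two things: stopping study visits and imaging, and withdrawing consent for data use.

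- For patients whom the investigator takes off study visits, and for patients who stop visits themselves but agree to it, continue to collect vital status, filter status (indwelling or retrieved, with date), symptomatic PE and major adverse events.
- Do this by telephone or record review at the 6-, 12-, 18- and 24-month time points that Section 7.7 already sets.
- State that these data enter the primary analyses.
- State that full withdrawal of consent still ends collection.

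The cost is protocol and consent wording and minor site time, with no new procedure or imaging. The reported rates may come out slightly less favourable, and events found by record review will be less fully imaged than those found at study visits.
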